16.4 Sample Size Determination

The proposed trial design is a randomized phase II trial with a 1:1 randomization ratio with the stratification variable noted in section 5.1. The primary endpoint for this trial is the 24-month complication rate, as defined above. The study will plan to enroll a total of 72 evaluable patients. An evaluable patient is defined as a patient who receives any dose of the protocol-defined radiotherapy. In this trial, we will accrue and randomize up to 96 patients over 3 years to account for ineligibility, cancellations (withdrawals prior to protocol therapy), major treatment violations, or other reasons, and treat a total of 82 patients in order to ensure 72 evaluable patients at 24 months.

This study is designed as a non-inferiority/superiority “hybrid” design using the approach of Freidlin et al.[36] It is estimated that approximately 2/3 of the patients will undergo reconstruction. For patients who undergo mastectomy with immediate reconstruction, the rate of unplanned surgical complications at the Mayo Clinic is ~15% (personal communications with [name] and [name] 6/2014), comparable to what has been reported in the literature in the modern era.[27]. The rate of grade 3 or greater late toxicity in this population is expected to be $\leq 1\%$ (Whelan ASCO 2011). For the purpose of designing this trial, we will assume a 10% complication rate in the control arm. We consider that a 10% increase of this rate in the experimental arm would be acceptable (i.e. a non-inferiority margin of 10%). Based on the results of the START-B clinical trial[9], it is also plausible that toxicities in the experimental arm may even be reduced with the shortened fractionation schedule. Therefore, a marginal *decrease* in complication rate in the experimental arm to 5% (i.e. marginal benefit margin of 5%) may be reasonably expected. Denote p_0 and p_1 as the 24-month complication rate in the control arm and experimental arm, respectively. The null hypothesis is that the complication rate in the experimental arm is inferior to the control rate of 10% by more than 10% (i.e. $H_0: p_1 - p_0 > 10\%$). The alternative hypothesis is that the complication rate in the experimental arm is non-inferior to the control rate of 10% (i.e. $H_A: p_1 - p_0 < 10\%$).

The primary analysis will occur after a minimum of 2-years following the enrollment of the last evaluable patient. The 24-month complication rate for each treatment arm will be estimated using exact binomial method along with a 1-sided 95% confidence limit. The approach of Freidlin et al. allows sequentially testing the hypotheses of non-inferiority and superiority in the same trial. Specifically, we will first test the non-inferiority hypothesis based on non-inferiority (NI) margin of 10%. If the upper bound of the 1-sided 95% confidence limit for $(p_1 - p_0)$ is larger than 10%,

then inferiority (of the experimental arm) cannot be ruled out. Otherwise, if the null hypothesis is rejected in favor of non-inferiority, then a test of superiority will be performed. Specifically, if the upper bound of the 1-sided 95% confidence limit for $(p_1 - p_0)$ is smaller than 0%, then superiority of the experimental arm is concluded; otherwise, if the upper bound of the 1-sided 95% confidence limit for $(p_1 - p_0)$ exceeds 0% but does not exceed 10%, non-inferiority without superiority will be concluded. No multiple-comparison adjustment is required for the two hypotheses tests.[36]

The operating characteristics of the proposed design are evaluated by carrying out 5,000 simulations. Using a one-sided type I error rate of 0.05 (corresponding equivalently to constructing a 1-sided 95% confidence limit), a study of 72 evaluable patients will have 80% power to reject the null hypothesis that the 24-month complication rate in the experimental arm is higher than that of the control arm by more than 10% (i.e. rule out inferiority) under the alternative hypothesis that the complication rate in the experimental arm is 5% less than that of the control arm (i.e. superiority). However, the design will have only 41% power when the two treatment arms are equivalent (i.e. the complication rate is 10% for both arms).

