5.0 Randomization Factors

5.1 Assignment of treatments will be balanced with respect to the presence of immediate reconstruction (mastectomy/immediate reconstruction vs mastectomy/no immediate reconstruction) using a biased-coin minimization algorithm.[29]

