16.0 Statistical Considerations and Methodology

This is an open label phase II randomized controlled trial to determine the safety of 15 fraction vs 25 fraction scanning beam proton radiotherapy after mastectomy in patients requiring regional nodal irradiation.

16.1 Primary Endpoint:

16.1.2 Primary endpoint: 24 month complicate rate, defined as the percentage of women randomized who develop one or more of the following events:

- 1) grade 3 or higher late adverse events
- 2) unplanned surgical intervention (not including planned serial fat grafting) in patients who undergo mastectomy with reconstruction.

16.2 Secondary Study Endpoints: The secondary aims of this study are to characterize acute and late adverse events including grade ≥ 2 pneumonitis and reconstruction failure rate, assess patient self-reported cosmesis, evaluate fatigue, breast pain, arm function and other patient reported outcomes, compare the locoregional control, disease free, overall survival. Blood will be collected for future studies exploring dose volume and genomic predictors of adverse cosmesis and biomarkers of cardiotoxicity.

The following definitions are used for the secondary endpoints of interest:

- *Acute adverse events* (up to 90 days post-RT): any adverse event, regardless of attribution, that occurs in the first 90 days post-RT.
- *Late adverse events* (up to 5 years post XRT): any adverse event that occurred after the first 90 days post-RT and up to 5 years post-RT.
- *Reconstruction failure* (up to 5 years post XRT): loss of the tissue expander or implant with the inability to replace it resulting in no final reconstruction or conversion to autologous reconstruction or revised with the addition of autologous reconstruction.[27, 28]
- *Patient Reported Outcomes/Quality of life*: Elements of the Patient-Reported Outcomes Version of the Common Terminology Criteria for Adverse Events (PRO-CTCAE) will be used for patient self-reporting of toxicities. The Breast Cancer Treatment Outcomes Scale (BCTOS) will be used to measure patient reported functional status (pain, mobility). Other measures of fatigue, pain, and arm function are listed in the appendix.
- *Patient self-reported cosmetic outcomes*: the patient self-reported outcome will be assessed using a modified Harvard Cosmesis Scale and a modified BCTOS at baseline, 2 years, and 5 years.

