16.6 Analysis Plan

The primary analysis will occur after a minimum of 2-years following the enrollment of the last evaluable patient.

16.61 Primary Analysis: The primary analysis will be to estimate the difference in the complication rate (grade 3+ toxicities, and unplanned surgical interventions) between the experimental arm and the control arm, which is defined as 24-month complication rate in experimental arm minus that in the control arm. All patients meeting the eligibility criteria who have signed a consent form and started treatment will be in the primary analysis. The complication rate will be estimated using a binomial estimator in both experimental arm and control arm, and a one-sided 90% confidence interval of the difference will be computed with normal approximation.

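### The primary comparison ignores the reconstruction factor used in randomisation and gives no result for reconstructed women, who on the planning rates supply nearly all primary events

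*Combined protocol and SAP*

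**What the plan says.** - **Endpoint (16.1.2).** The 24-month rate is "defined as the percentage of women randomized who develop one or more of the following events". The first component, "grade 3 or higher late adverse events", can occur in any woman. The second is "unplanned surgical intervention (not including planned serial fat grafting) in patients who undergo mastectomy with reconstruction".
- **Planning rates (16.4).** "It is estimated that approximately 2/3 of the patients will undergo reconstruction". For those with immediate reconstruction, "the rate of unplanned surgical complications at the Mayo Clinic is ~15" per cent. Grade 3 or greater late toxicity is expected in at most 1%. The control rate is taken as 10%.
- **Margin (16.4).** "We consider that a 10% increase of this rate in the experimental arm would be acceptable (i.e. a non-inferiority margin of 10" per cent). It is applied to the single difference p1 − p0 in all women, with a one-sided 95% limit.
- **Randomisation (5.1).** "Assignment of treatments will be balanced with respect to the presence of immediate reconstruction". Section 16.4 calls this the stratification variable.
- **Primary analysis (16.61).** "The complication rate will be estimated using a binomial estimator in both experimental arm and control arm", followed by a normal-approximation interval for the difference, here one-sided 90%. The reconstruction factor does not appear.
- **Other analyses (16.62).** Late adverse events and reconstruction failure are summarised by arm only. No section gives the primary endpoint by reconstruction status.

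**The concern.** A factor important enough to balance in the randomisation is left out of the analysis. It also marks off the women who can have the dominant component of the endpoint. A pooled difference averages the women at risk of unplanned surgery with a group expected to have almost no events, so the excess excluded in the pooled population is smaller than the excess excluded in reconstructed women.

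This bears on what the trial may claim. Section 1.3 describes the feasibility of hypofractionation with immediate implant reconstruction as critical to understand, and 2.1.2 asks whether the complication rate is acceptable and merits further study. If the report says that a 10-point excess was excluded, readers will apply that to reconstructed women. The plan produces no figure to show whether they may. A breakdown added after the results are known would carry less weight than one fixed in advance.

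**Working it through.** **Inputs.** 72 evaluable, 1:1, so 36 per arm; margin 10 points; one-sided 0.05; control 10%; alternative 5%; reconstruction share 2/3; surgery 15% in reconstructed women; grade 3+ toxicity 0–1% (all 16.4). A 2/3 share gives 24 reconstructed and 12 other women per arm.

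**1. The plan's own power.** Power = Φ[(0.10 − (p1 − p0))/SE − 1.645], with SE = √[(p1(1−p1) + p0(1−p0))/36].
- 5% versus 10%: SE = √(0.1375/36) = 0.0618; Φ(0.15/0.0618 − 1.645) = 78.3%. Exact enumeration gives 79.4%. The plan states 80%.
- 10% versus 10%: SE = √(0.18/36) = 0.0707; Φ(0.10/0.0707 − 1.645) = 40.9%. Exact enumeration gives 41.7%. The plan states 41%.

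The stated power is reproduced with a crude pooled test at one-sided 0.05. At 0.10 the figures would be about 87–88% and 55–57%.

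**2. Where the events fall.** Surgery alone gives 2/3 × 15% = 10.0%, which matches the assumed control rate. With 1% toxicity added independently in every woman:
- reconstructed: 1 − 0.85 × 0.99 = 15.85%, contributing 2/3 × 15.85% = 10.57%
- others: 1/3 × 1% = 0.33%
- total 10.9%; reconstructed share of women with an event = 10.57/10.9 = 96.9%

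With no toxicity the share is 100%.

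**3. The margin on the reconstructed scale.** Let f be the reconstruction share. If all excess falls in reconstructed women, the boundary there is 10/f points.

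| Share f | Equivalent excess in reconstructed women |
|---|---|
| 50% | 20 points |
| 2/3 | 15 points (15% to 30%) |
| 80% | 12.5 points |

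If other women carry an assumed 2-point excess, the value at 2/3 is (10 − 2/3)/(2/3) = 14 points.

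**4. What a pass excludes.** Take 3 experimental and 4 control events, all in reconstructed women, with one-sided 95% Wald limits.
- Pooled, 36 per arm: −2.78 + 1.645 × 6.98 = 8.7 points. This passes.
- Reconstructed, 24 per arm: −4.17 + 1.645 × 10.17 = 12.6 points.

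With 2 versus 2 events the limits are 8.9 and 13.1 points.

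**5. Operating characteristics** (24 + 12 per arm, no events in other women, exact enumeration, 95% limit).

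| True rates in reconstructed women, control vs experimental | Crude pooled | Stratified | 10-point test in reconstructed only |
|---|---|---|---|
| 15% vs 7.5% (design alternative) | 79.7% | 80.7% | 63.8% |
| 15% vs 15% (equality) | 41.2% | 44.3% | 27.0% |
| 15% vs 25% (+10 points) | 10.6% | 12.6% | 5.8% |
| 15% vs 30% (+15 points, pooled null boundary) | 4.6% | 5.7% | 2.3% |

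Entries are the chance of declaring non-inferiority. With the 90% limit of 16.61, the crude entries for +10 and +15 points become 19.7% and 9.7%.

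**6. Why stratifying helps a little.** At 10% in both arms, the ratio of stratified to crude variance is [(2/3)² × 2 × 0.1275/24] / [2 × 0.09/36] = 0.944, about 6% less.

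**The case against.** **The margin is on the right scale.** Control rate and margin are both set for the pooled population. A rise from 10% to 20% there is the same doubling as 15% to 30% in reconstructed women. No section promises a 10-point margin for reconstructed women, so the 10.6% in step 5 is not a type I error of the planned test. This stands, and the 10-point pooled rule should stay.

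**A reader might infer that the trial would accept a 15-point excess.** The documents do not support that. Fifteen points is the edge of the null, where the crude rule passes about 4.6% of the time. With 4 control events at most 3 experimental events pass at the 95% limit, so no observed excess passes at that count.

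**A reader might infer that leaving out the factor favours non-inferiority.** It does not. Under equality the crude analysis has slightly lower power, 41% against 44%.

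**A reader might infer that primary events are confined to reconstructed women.** They are not. Grade 3+ late events count in anyone, and 16.622 counts late events regardless of attribution. The 97–100% share is a forecast from the planning rates. Also, 16.1.2 speaks of reconstruction while 5.1 speaks of immediate reconstruction; surgery after a delayed reconstruction could arguably count in the other stratum.

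**The stratum is small.** With 24 per arm, a 10-point test has about 25–27% power under equality. It cannot be confirmatory. It can still report what was and was not excluded.

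**Conclusion.** The point holds as a gap in analysis and reporting. The margin is not in error. The pooled test is coherent and its type I error is controlled. What is missing is use of the 5.1 factor in the primary estimate, and any pre-specified primary-endpoint result for the women expected to supply about 97–100% of those with events. Without that result, a pooled non-inferiority finding leaves open whether a 10-point excess in reconstructed women has been excluded; the pooled null boundary corresponds to about 15 points there.

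The figures assume 36 per arm, a 2/3 share, all excess in reconstructed women, Wald limits at one-sided 95%, and toxicity of 0–1%. The share is an estimate that the plan does not fix; 80% gives 12.5 points and 50% gives 20. More grade 3+ late events in other women would weaken the concentration. Stratifying does not change the 15-point equivalence; the stratum limit is what discloses it.

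**What to change.** In 16.61:

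1. Estimate p1 − p0 and its one-sided limit stratified by the 5.1 factor, for example with a Mantel-Haenszel risk difference. Keep the 10-point pooled margin as the decision rule.
2. Pre-specify the same difference and limit within the immediate-reconstruction stratum, labelled supporting and non-confirmatory.
3. State that the pooled claim applies to the enrolled mix, and that the stratum's limit shows what was excluded in reconstructed women. State how delayed reconstruction is classified.
4. Reconcile the one-sided 95% limit in 16.4 with the 90% interval in 16.61 and use one level throughout. The stated power corresponds to 95%.

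**Cost.** SAP wording and one table; no extra patients or data. At the 95% limit, power rises from about 41% to 44% under equality and from about 80% to 81% at the design alternative. With sparse events, the normal-approximation error at the boundary moves from about 4.6% to 5.7%, slightly above the nominal 5%, so the interval method should be checked by simulation before it is fixed. A wider limit will be reported for reconstructed women.

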16.6 Analysis Plan

The primary analysis will occur after a minimum of 2-years following the enrollment of the last evaluable patient.

16.61 Primary Analysis: The primary analysis will be to estimate the difference in the complication rate (grade 3+ toxicities, and unplanned surgical interventions) between the experimental arm and the control arm, which is defined as 24-month complication rate in experimental arm minus that in the control arm. All patients meeting the eligibility criteria who have signed a consent form and started treatment will be in the primary analysis. The complication rate will be estimated using a binomial estimator in both experimental arm and control arm, and a one-sided 90% confidence interval of the difference will be computed with normal approximation.

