4.0 Test Schedule

Assessments, tests and procedures	Treatment			Observation ⁷
	Baseline ²	Last day of treatment (+/- 2 days)	12 weeks (+/- 8 weeks) post-radiation	12 months (+/- 3 month) post completion of radiotherapy, 24 months (+/- 3 months), 36 months (+/- 3 months), and at 5 years (+/- 3 months)
History and Physical exam (including breast assessment/exam) ¹	X	X	X	X
Mammogram	X ¹⁰			X ¹¹
Cosmesis ,QOL Outcome Assessment and Breast-Q ¹⁶ (see section 11.3 and Appendix)	X ¹³	X	X	X
Digital Photograph	X	X	X	X
Review of surgical specimen(s) to confirm eligibility	X ³			
Echocardiography ^{9, 14}	X ¹³			X ⁸
Radiation toxicity assessment (see section 10.4)	X	X	X	X
Serum pregnancy test	X ⁴			
Blood specimen ^{5, 17, R}	X ¹⁵	X	X	X ¹²
Surgical tumor specimen ^{6, 18, R}	X			

1. A general history & physical must be done \leq 8 weeks prior to registration. This should include an assessment of ECOG performance status (see Appendix I).

2. Following definitive surgical resection and adjuvant chemotherapy if indicated, prior to the start of radiation.
3. Outside pathology must be reviewed at the treating institution.
4. For women of childbearing potential only, must be within 7 days of radiotherapy
5. See section 14 for collection time and preparation of samples
6. See section 17 for collection time and preparation of samples
7. Patients that cannot come back to Mayo Rochester within the time constraints of the follow-up schedule; efforts to obtain outside records and send QOL's to be completed will occur, however the required items may not be captured.
8. Ideally 6-12 months post radiotherapy in HER2 positive patients treated with HER2 directed therapy and in patients treated with anthracycline as part of routine clinical care. Only followed for Echos 1 year post therapy.
9. Co-enrollment on IRB 15-007443 (echo protocol) is required in Rochester while open
10. Completed \leq 12 months prior to study entry
11. As clinically indicated
12. At 12 months post-treatment visit only to coincide with echocardiography.
13. Should be \geq 14 days since last chemotherapy
14. After closure of IRB 15-007443 (echo protocol) echocardiography tests will be performed only in left sided patients previously treated with anthracycline and/or HER2 directed systemic therapy. This correlative component will occur at Rochester Mayo only.
15. Baseline blood collection will be drawn through co-enrollment on IRB 15-000136 (Radiation Oncology Outcomes Registry and Biobanking Study).

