7.3 Dose Specifications

7.31 Arm 1 post-mastectomy plus regional nodal irradiation

7.311 Chest wall and regional nodes: 50 Gy (RBE) in 25 fractions of 2 Gy (RBE)

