7.32 Arm 2 post-mastectomy plus regional nodal irradiation

7.321 Chest wall and regional nodes: 40.05 Gy (RBE) in 15 fractions of 2.67 Gy (RBE)

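### The earliest permitted primary analysis is counted from enrolment, but the 24-month visit is counted from the end of radiotherapy and the endpoint states no time origin; the resulting bias is small and cheap to remove

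*Combined protocol and SAP*

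**What the plan says.** Sections 16.4 and 16.6 carry the same timing rule: "The primary analysis will occur after a minimum of 2-years following the enrollment of the last evaluable patient". It is a floor, counted from enrolment.

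The data that feed the endpoint are dated differently. The observation column of Section 4.0 places the visits at "12 months (+/- 3 month) post completion of radiotherapy, 24 months (+/- 3 months", so the 24-month visit may fall from 21 to 27 months after radiotherapy ends. Section 16.2 defines a late adverse event, the first component of the primary endpoint, as "any adverse event that occurred after the first 90 days post-RT and up to 5 years post-RT".

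The endpoint itself, in Section 16.1, reads "Primary endpoint: 24 month complicate rate, defined as the percentage of women randomized who develop one or more of the following events". It does not say when the 24 months begin.

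On estimation, Section 16.4 says "The 24-month complication rate for each treatment arm will be estimated using exact binomial method", and Section 16.61 also uses a binomial estimator, applied to all eligible, consented patients who started treatment. Evaluability in Section 16.4 requires only some protocol radiotherapy. Neither section says what happens to a patient whose 24 months are incomplete at the cut. Disease-free and overall survival, by contrast, are to be estimated by Kaplan-Meier.

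**The concern.** The analysis clock starts at enrolment and the data-collection clock starts at the end of radiotherapy, so the two differ by the wait for treatment plus 15 or 25 daily fractions. An analysis run at the floor would include patients who have not completed 24 months after radiotherapy and may not have had the visit. A simple proportion cannot represent partial follow-up: such patients are either counted as complication-free or left out.

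Counting them as complication-free lowers both observed rates and shrinks the difference. At the non-inferiority boundary (20% against 10%) that moves the estimate below the 10-point margin, which is the non-conservative direction in a safety comparison. Leaving them out uses part of the allowance between 82 treated and 72 evaluable patients. The question is how large either effect is.

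**Working it through.** **Inputs from the plan.** 82 treated patients, accrual over 3 years, 72 evaluable patients (36 per arm at 1:1), control rate 10%, alternative 5%, margin 10 points, one-sided alpha 0.05 (all Section 16.4); visit window of 3 months either side (Section 4.0).

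**Assumptions.** Even accrual of the 82 over 36 months. Enrolment to end of radiotherapy takes L = 1 to 3 months; the plan does not give this lag. Courses of 15 and 25 fractions last about 3 and 5 weeks, as in the comparison trial described in Section 1.3. Half of all events fall after month 12, spread evenly over months 12 to 24; the plan has no figure for this.

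**1. The plan's own power.** Power = Φ[(0.10 − (p1 − p0))/SE − 1.645], with SE = √[(p0(1 − p0) + p1(1 − p1))/36].
- 10% against 5%: 78.3% (exact enumeration of the normal-approximation limit gives 79.4%); the plan says 80%.
- 10% against 10%: 40.9% (exact 41.7%); the plan says 41%.

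The stated figures are reproduced to within 2 points.

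**2. Is there a gap with no start delay?** A 3-week course is 0.69 months and a 5-week course 1.15 months. At the 24-month floor the last patient is 24 − 0.69 = 23.3 or 24 − 1.15 = 22.85 months past radiotherapy. The gap therefore exists in both arms even if treatment starts on the day of enrolment.

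**3. Patients affected.** Accrual is 82/36 = 2.28 per month.
- Short of 24 months after radiotherapy: 2.28 × L = 2.3 to 6.8, about 2 to 7.
- Visit window still open: 2.28 × (L + 3) = 9.1 to 13.7, about 9 to 14 of 82 (11 to 17%).
- Window not yet open: none, since L does not exceed 3 months and the window opens at month 21.

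A wider assumption, a start delay of 0 to 12 weeks plus an average 4-week course, gives about 2 to 8 and 9 to 15.

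**4. Bias if events are counted by date.** The patients short of 24 months are a fraction L/36 of the total and lack L/2 months on average; each month in the second year carries 0.5/12 of all events.
- L = 1: (1/36)(0.5)(0.5/12) = 0.0006, so 10 points appears as 9.99.
- L = 3: (3/36)(1.5)(0.5/12) = 0.0052, so 10 points appears as 9.95.

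**5. Ceiling.** Every patient with an open window is unseen, counted event-free, and loses all events after month 12.
- L = 1: 10 × (1 − 0.5 × 4/36) = 9.44.
- L = 3: 10 × (1 − 0.5 × 6/36) = 9.17 (9.15 with 14 whole patients).

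**6. False non-inferiority at 20% against 10%.** By the normal approximation, the nominal 5.00% becomes at most 5.06% under step 4 and 5.7 to 6.2% under step 5. By exact enumeration it goes from 5.5% to 6.3 to 6.8% under step 5. These use the one-sided 95% limit of Section 16.4.

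**The case against.** The strongest reply is that the plan sets a minimum, not a date. Section 16.4 speaks of 72 patients evaluable at 24 months, so complete 24-month data are plainly intended and the sponsor is free to wait. That stands as a reading of intent. It does not close the gap, because nothing requires the wait, and in an open-label trial the cut should not be left to discretion.

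Second, the endpoint has no stated origin. If its 24 months ran from randomisation, the floor would cover the calendar period. This also stands, and it makes the missing origin part of the point. The collecting visit would still be dated from the end of radiotherapy.

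Third, the visit can be made from month 21, so under the 1-to-3-month assumption every window is already open at the floor and some visits may be done. This stands, and it makes 9 to 14 an upper bound.

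A reader might infer that the plan triggers the analysis before the last patients are assessed, or that non-inferiority is materially favoured. The documents support neither. The first turns a floor into a fixed date. The second needs the ceiling in step 5, and no rule in the plan says that unseen patients are counted event-free. Nor is the direction general: under the design alternative of 10% against 5%, shrinkage moves a 5-point benefit towards the margin, lower variance offsets this, and power moves only from 78.3% to at most 79.1%. If patients short of 24 months are dropped instead, 2 to 7 fit within the reserve of 82 − 72 = 10, provided other losses have not used it.

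**Conclusion.** The mismatch is real and its effect is small. The plan permits a primary analysis when about 2 to 7 of 82 treated patients are short of 24 months after radiotherapy, and it gives no rule for them. The likely distortion of a 10-point difference is 0.01 to 0.05 points when events are counted by date. About 0.6 to 0.8 points is a ceiling, not an expectation.

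The patient counts rest on even accrual and a lag of 1 to 3 months; the bias figures also rest on the assumed half of events after month 12. None of these comes from the plan. The existence of the gap needs only the course lengths. The point is worth making because the correction is cheap and removes a discretionary cut on incomplete endpoint data, not because the trial's conclusion is under threat.

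**What to change.** - **Section 16.1:** state that the 24 months run from completion of radiotherapy, and count events by their date up to that point.
- **Sections 16.4 and 16.6:** set the primary analysis after every evaluable patient has completed the 24-month post-radiotherapy visit, or its window (27 months after completion of radiotherapy) has closed.
- **Section 16.61:** say how a treated patient whose window closes without a visit enters the proportion.

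Cost: a wording change, and an earliest analysis date about 4 to 6 months later (27 + 1 − 24 = 4; 27 + 3 − 24 = 6). Sample size, treatment and the visit schedule do not change.

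### Section 16.61 computes a one-sided 90% limit for the primary difference, but the decision rule, alpha and power in Section 16.4 all rest on a one-sided 95% limit; deciding by 16.61 doubles the nominal false non-inferiority rate.

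*Combined protocol and SAP*

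**What the plan says.** Section 16.4 (Sample Size Determination) gives the design and the decision rule. The operating characteristics are obtained "Using a one-sided type I error rate of 0.05 (corresponding equivalently to constructing a 1-sided 95% confidence limit"), and on that basis "a study of 72 evaluable patients will have 80% power to reject the null hypothesis" when the experimental arm is 5 points better. Power falls to 41% when both arms are at 10%. The rule is sequential and uses one limit throughout, the upper one-sided 95% limit for experimental minus control. Above 10%, inferiority is not ruled out. Below 0%, superiority is concluded. If it "exceeds 0% but does not exceed 10%, non-inferiority without superiority will be concluded".

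Section 16.61 (Primary Analysis, under 16.6) defines the same difference in the same direction and then states that "a one-sided 90% confidence interval of the difference will be computed with normal approximation". It gives no alpha and no threshold, and does not refer back to the rule in 16.4. It is also the only place that names a computational method for the interval of the difference; the exact binomial method in 16.4 is attached to the rate in each arm.

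**The concern.** A one-sided 90% limit corresponds to alpha 0.10, twice the design level. The plan thus gives two confidence levels for the one number that decides the trial: one in the section with the decision rule, the other in the section an analyst would program from. The same data could lead to opposite primary conclusions depending on which section is followed.

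The error at stake is the important one here. The primary goal (Section 2.1) is to judge whether the 15-fraction complication rate is acceptable relative to 25 fractions. A looser limit makes it easier to accept a schedule that is in truth worse by the whole margin. The trial is open label, so leaving the level unsettled until data are available also leaves the result open to challenge.

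**Working it through.** **Inputs, all from Section 16.4.**
- Control rate: "we will assume a 10% complication rate in the control arm".
- Experimental rate under the design alternative: 5%, from "complication rate in the experimental arm to 5% (i.e. marginal benefit margin of 5"%).
- Margin: 10 points, "i.e. a non-inferiority margin of 10"%.
- Sample size: 72 evaluable. With "The proposed trial design is a randomized phase II trial with a 1:1 randomization ratio", that is 72 / 2 = 36 per arm.

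**Formula.** The normal-approximation upper limit, as named in 16.61, is taken as the unpooled Wald limit:

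U = (p̂1 − p̂0) + z × √[p̂1(1 − p̂1)/36 + p̂0(1 − p̂0)/36]

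with z = 1.645 for one-sided 95% and z = 1.282 for one-sided 90%. Non-inferiority is declared if U ≤ 0.10, superiority if U < 0. Each probability below is the sum of the binomial probabilities of all pairs of event counts that meet the condition.

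**Step 1: closed-form check of the stated power.** Power ≈ Φ[(0.10 − δ)/SE − z], where δ is the true difference.
- 5% vs 10%: SE = √[(0.05 × 0.95 + 0.10 × 0.90)/36] = 0.0618; (0.10 + 0.05)/0.0618 = 2.427. At 95%: Φ(2.427 − 1.645) = 78.3%. At 90%: Φ(2.427 − 1.282) = 87.4%.
- 10% vs 10%: SE = √[(0.09 + 0.09)/36] = 0.0707; 0.10/0.0707 = 1.414. At 95%: Φ(1.414 − 1.645) = 40.9%. At 90%: Φ(1.414 − 1.282) = 55.3%.

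**Step 2: exact enumeration, 36 per arm.**

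| True rates (experimental vs control) | Conclusion | Plan states | One-sided 95% | One-sided 90% |
|---|---|---|---|---|
| 5% vs 10% | non-inferior | 80% | 79.4% | 88.2% |
| 10% vs 10% | non-inferior | 41% | 41.7% | 56.8% |
| 20% vs 10% | non-inferior (false) | alpha 0.05 | 5.5% | 11.0% |
| 10% vs 10% | superior (false) | alpha 0.05 | 5.9% | 10.6% |

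A 5,000-run simulation at 95%, the number of runs the plan used, gave 80.4% and 42.3%. Both stated powers are therefore reproduced at one-sided 95%, and neither at one-sided 90%. A continuity-corrected 90% limit gives 80.4% at 5% vs 10% but 44.6% at equality, so it does not fit both figures either.

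**Step 3: data sets on which the sections disagree.**
- 4/36 vs 4/36: difference 0, SE 0.0741. U = 1.645 × 0.0741 = 12.2% (inferiority not ruled out) or 1.282 × 0.0741 = 9.5% (non-inferior).
- 3/36 vs 3/36: SE 0.0651. U = 10.7% or 8.3%, again opposite verdicts.
- 0/36 vs 2/36: difference −5.6 points, SE 0.0382. U = +0.7% (non-inferior, not superior) or −0.7% (superior).

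These are ordinary results: the assumed 10% rate implies 3.6 events per arm. With both arms truly at 10%, the two levels give different non-inferiority verdicts with probability 56.8% − 41.7% = 15.1%.

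**The case against.** The strongest reply is that only Section 16.4 contains a decision rule. It names the 95% limit at each step, while 16.61 speaks of estimating the difference and attaches no conclusion to its interval. On that reading the 90% interval is descriptive and no error rate changes. This stands in part: the inflation, including that of the superiority test, occurs only if the 16.61 limit is used for the decision. But 16.61 carries the title Primary Analysis, offers no other interval for the difference and does not call its interval descriptive.

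A second reply is that a two-sided 90% interval was meant. Its upper end is the one-sided 95% limit, so the two sections would agree. This is plausible and fits the reproduced power, but the text says one-sided, so it still needs correcting.

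Third, power rises under 16.61. That is true: the stated 80% and 41% would no longer describe the analysis, but no power is lost. The gain comes entirely from relaxing alpha beyond what 16.4 allows.

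Fourth, the exact multiple depends on the number analysed. Section 16.61 includes all eligible, consented patients who started treatment, and 16.4 plans to treat 82. If all 82 counted, at 41 per arm, false non-inferiority at 20% vs 10% would be 6.3% at 95% and 10.2% at 90%, a ratio of about 1.6. The nominal doubling, 0.05 to 0.10, is unaffected.

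**Conclusion.** The concern holds. Sections 16.4 and 16.61 prescribe different confidence levels for the same primary comparison, and the plan's own power figures identify one-sided 95% as the design level.

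The cost of deciding by 16.61 is a false non-inferiority rate of about 11% instead of about 5.5% at the margin, and a false superiority rate of about 10.6% instead of 5.9% at equal rates. These figures assume 36 per arm, a 10% control rate and an uncorrected Wald limit. The size of the inflation varies with the analysis set; its direction does not. Because the primary conclusion can turn on which section is followed, this must be corrected.

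**What to change.** In Section 16.61, change the stated level to a one-sided 95% upper confidence limit for experimental minus control, or equivalently to the upper end of a two-sided 90% interval. Add one sentence saying that this is the limit compared first with 10% and then with 0% under the rule in 16.4. If the team also wants a one-sided 90% interval, label it descriptive.

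The cost is a line or two of wording, with no change to sample size, data collection or stated power. It should be made and dated before the primary analysis, so that the level is not chosen with the results in view.
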